7 STATISTICAL METHODOLOGY

7.1 Aim 1:

7.1.1 Descriptive statistics

Descriptive statistics will be used to summarize cross sectional survey results as well as baseline demographic and other exposure variables. This will include number and percentage for categorical variables; for continuous variables mean and standard deviation will be tabulated, with median, first quartile, and third quartile included in at least internal reports.

7.1.2 Association of COVID attitudes, beliefs, and practices with outcomes

Linear regression models or generalized linear regression models (GLM) with robust standard errors will be used to assess the association between the primary and secondary outcomes and COVID attitudes, beliefs, and practices, adjusting for baseline demographic information. Each outcome will be modeled separately.

7.1.3 Variations in outcomes across type of employee

To assess how different types of healthcare providers are coping with COVID related mental distress and changes, we will use linear models with robust standard error, testing for a difference in reported distress levels across provider type while adjusting for baseline demographics. Employee categories will include:

- provider (physician and advanced practice providers such as physician assistants and nurse practitioners);
- nursing;
- social support services;
- other patient-facing, including pharmacy, medical assistants, and technicians; and
- non-clinical, including officer work, educators, senior management, and other.

7.2 Aim2:

7.2.1 Primary analysis

The effects of the intervention will be modeled separately in patients and providers/staff. **Linear regression with robust standard errors will be used to determine whether the primary outcome differs between CC+ vs CC**, adjusting for the baseline score as a precision variable. Multiple imputation will be used to account for missing data (see 7.3).

7.2.2 Secondary analyses

All outcomes will be modeled separately in the patient and provider/staff populations. Linear regression will be used to estimate the difference in means for continuous outcomes; for binary outcomes, GLM models with an identity link will allow for the estimation of the difference in proportions. Robust/sandwich standard errors will be used to allow for departures of the observed standard errors from classic model assumptions.

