6.2 Secondary endpoints

- Secondary outcomes include suicide ideation; suicidal ideation and behavior will be measured as score at 6 months using the Columbia Suicide Severity Rating Scale (C-SSRS). Scores range from 0-6. Risk factors for suicide will be measured by the Interpersonal Needs Questionnaire (INQ-15). This survey measures feelings of perceived burdensomeness and thwarted belongingness; scores range from 15 to 105. The changes from baseline thwarted belongingness and perceived burdensomeness scales will be analyzed separately.
- Depression will be measured as score at 6 months in the Patient Health Questionnaire-9 (PHQ-9); this questionnaire results in a score between 0-27, with higher scores indicating worse depression. A score of 5-9 is considered minimal depression, 10-14 is considered mild major, 15-19 is moderate major, and ≥ 20 is severe major. Analysis will be based on the continuous score, with categories examined in exploratory/sensitivity analysis.

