6.3 Exploratory endpoints

- Suicide attempts and lethal means will be summarized and compared across treatment arms. Questions will include the number of attempts and aborted attempts and lethal means.
- Psychological stress will be measured using the NIH Toolbox and assessed as change from baseline. This instrument results in a continuous T-score outcome.
- Changes in alcohol and illicit drug use will be described. Participants will be asked if they are current, ever, or never user of a variety of substances (tobacco, alcohol, marijuana, other illicit drugs), as well as the amount and frequency of use for current users. Participants will be asked about whether or not the amount they use has changed. Changes from baseline to 6 months in the current/ever/never question will be summarized for each substance, as well as reporting the number and percentage of participants with any increase or any decrease.
- The GAD-7 scale will be used to measure anxiety. Participants respond to seven items and receive possible scores of 0-21.
- Attendance at mental healthcare appointments will be measured as a dichotomous variable (yes/no) at 6 months through self-report.

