6.5 Covariates

Potential effect modifiers will be assessed and include age, sex, gender identity, sexuality, race/ethnicity, religion, employment, urban/rural residence, drug/alcohol use, suicidal ideation at baseline, baseline depression score, baseline anxiety score, baseline stress score, baseline quality of life, measures of socioeconomic status and/or other variables related to the specified outcomes of interest.

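### SAP 7.2.2 names no baseline covariate for the secondary and exploratory scales, although 7.2.1 adjusts loneliness for its baseline and every scale's baseline is collected: an avoidable loss of precision, not a bias

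*SAP*

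**What the plan says.** SAP 7.2.1 fits loneliness by linear regression with robust standard errors, "adjusting for the baseline score as a precision variable". SAP 7.2.2, which opens by referring to all outcomes, states "Linear regression will be used to estimate the difference in means for continuous outcomes" and names no covariate. Protocol 13.1 likewise names linear regression and GLMs for the secondary outcomes without covariates.

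The outcome forms differ by scale:

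- C-SSRS (SAP 6.2): "suicidal ideation and behavior will be measured as score at 6 months using the Columbia Suicide Severity Rating Scale (C-SSRS"). Protocol 8.3.1 defines it as a change from baseline.
- PHQ-9 (SAP 6.2): "Depression will be measured as score at 6 months in the Patient Health Questionnaire-9 (PHQ-9").
- INQ (SAP 6.2): "The changes from baseline thwarted belongingness and perceived burdensomeness scales will be analyzed separately".
- Stress (SAP 6.3): "Psychological stress will be measured using the NIH Toolbox and assessed as change from baseline". Protocol 8.3.4 also uses a change.
- GAD-7 (SAP 6.3): "The GAD-7 scale will be used to measure anxiety", with no statement of score or change.

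SAP 6.5 is headed as a list of covariates and includes "baseline depression score, baseline anxiety score, baseline stress score", but as potential effect modifiers, and it omits the INQ. Protocol Table 2 collects all five instruments in the Aim 1 survey and again in the Aim 2 outcome survey. The Aim 1 survey comes before Aim 2 consent and randomisation (Protocol 4.2 and Table 1).

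**The concern.** The plan accepts for loneliness that the baseline score buys precision, then does not say whether the same holds for suicidality, INQ, depression, stress and anxiety, where the baseline is also in hand. An unadjusted 6-month score ignores the baseline. A raw change subtracts all of it, which at equal SDs is noisier than ignoring it when the correlation is below 0.5. An analyst following 7.2.2 literally would get wider intervals than the data need. An analyst who adjusts would be making a choice that the SAP does not record.

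**Working it through.** **Inputs from the documents.** Two-sided alpha 0.05 (Protocol 13.1). 165 per arm in each stratum, at least 70% retained, 80% power for 5 units of loneliness (Protocol 13.2, SAP 5). Twenty hot-deck data sets, with donors matched on arm, baseline loneliness tertile and population, pooled by Rubin's rule (SAP 7.3).

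**Assumed, because the documents do not give them.** Baseline to 6-month correlation ρ = 0.3, 0.5 or 0.7. Ratio k of baseline SD to 6-month SD = 0.7, 1.0 or 1.3.

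**The plan's own figure.** 165 × 0.70 = 115.5 per arm. Then 80% power for 5 units needs SD = 5 × √(115.5/2) / (1.960 + 0.842) ≈ 13.6. No SD is stated, so the 80% cannot be confirmed. It concerns loneliness only, and nothing below depends on it.

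**Complete data.** Take the variance of the 6-month score comparison as 1. The adjusted comparison has 1 − ρ² and raw change has 1 + k² − 2kρ. The cut against change is 1 − adjusted/change.

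| ρ | adjusted | cut vs score | change, k = 0.7 (cut) | change, k = 1.0 (cut) | change, k = 1.3 (cut) |
|---|---|---|---|---|---|
| 0.3 | 0.91 | 9% | 1.07 (15%) | 1.40 (35%) | 1.91 (52%) |
| 0.5 | 0.75 | 25% | 0.79 (5%) | 1.00 (25%) | 1.39 (46%) |
| 0.7 | 0.51 | 49% | 0.51 (0%) | 0.60 (15%) | 0.87 (41%) |

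**With missing data and the planned hot deck.** Donors are matched on loneliness tertile, not on the scale's own baseline, so imputed values carry little of that baseline and the gain shrinks. This was simulated with 165 per arm, 30% of 6-month outcomes missing completely at random, 20 draws, and a correlation of 0.5 between the scale's baseline and loneliness. The Rubin-pooled variance, which the planned test uses, falls by about 4%, 11% and 22% against the 6-month score. The actual sampling variance of the estimate falls somewhat more (about 5%, 21% and 31% in one run), but the pooled variance sets the p-values and intervals.

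**Power.** For an effect with 80% power adjusted, unadjusted power is Φ(2.8016 × √(1 − cut) − 1.960):

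- cut 4%: Φ(2.745 − 1.960) = Φ(0.785) = 78%
- cut 11%: Φ(2.643 − 1.960) = Φ(0.683) = 75%
- cut 22%: Φ(2.474 − 1.960) = Φ(0.514) = 70%

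**Where adjustment can lose.** At k = 0.7 and ρ = 0.7, with the hot deck imputing scores, the adjusted estimate has about 3–5% more sampling variance than raw change. If raw change is instead computed from imputed changes, the adjusted estimate based on imputed scores has about 28% more.

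**Score or change as the outcome.** With the baseline in the model, replacing the score by the change lowers the baseline coefficient by 1 and leaves the arm coefficient as it was. This holds if the 6-month score is imputed and the change derived from it. If a donor's change is drawn, the two adjusted estimates differ: the SD of the difference was 0.05–0.07 against a standard error of 0.10–0.13. SAP 7.3 speaks of sampling 6-month outcomes and does not say which quantity is drawn for scales analysed as changes.

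**Missing baselines.** Aim 1 respondents may skip questions (Protocol 15.1). With 5–10% of a scale's baselines also missing at random (k = 1.0), filling with the mean pooled over arms kept a cut in sampling variance against the score of about 5%, 13–16% and 29–32%. Dropping those people left about 0–3%, 9–14% and 28–32%.

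**The case against.** The strongest reply is that this is optional efficiency. Unadjusted comparisons are legitimate after randomisation, Protocol 13.1 relies on randomisation and stratification to deal with confounding, the SAP treats stress and GAD-7 as exploratory, and 7.2.1 may have been meant to carry over. All of that stands, and it limits the point to precision and prespecification. It does not remove the point, because nothing in 7.2.2 says that the model carries over.

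Some stronger readings are tempting, and the documents do not support them:

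- *The secondary comparisons are biased or underpowered.* Leaving out a baseline covariate does not bias a randomised comparison, and the documents claim power only for loneliness. Bias from missing outcomes is a separate matter, which SAP 7.4 takes up.
- *The SAP rules adjustment out.* It is silent, which is different.
- *The complete-data gain of 9–49% would be realised.* Not with 30% missing and donors matched only on loneliness.
- *Nothing covers missing baselines.* Protocol 13.4 allows multiple imputation of missing data in general. Only SAP 7.3 is confined to 6-month outcomes.
- *C-SSRS gains as much as the other scales.* Protocol 8.3.1 uses the Lifetime-Recent screener at baseline and Since Last Contact at 6 months, which probably lowers the correlation.

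**Conclusion.** The gap in the text is certain; the size of the gain rests on assumed correlations and SD ratios. Against a 6-month score, as planned for C-SSRS and PHQ-9, adjustment helps at every correlation examined: modestly at 0.3, materially at 0.7. Against raw change, as planned for the INQ subscales and stress, it helps in most settings. It is about neutral with complete data when the baseline SD is well below the 6-month SD and the correlation is high, and there it can lose precision under the hot deck. The missingness was simulated as completely at random. This is a worthwhile improvement to the secondary analyses, not a threat to their validity.

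**What to change.** 1. In SAP 7.2.2, state that each scale analysed by linear regression (both INQ subscales, PHQ-9, GAD-7, perceived stress, and C-SSRS if its score is analysed that way) is modelled with arm and that scale's own baseline score, with robust standard errors, as in 7.2.1.
2. In SAP 7.3, state that the hot deck imputes the 6-month score and that any change is derived from it, so that the adjusted score and change models give the same arm effect.
3. Give one outcome form per scale, including GAD-7, and align SAP 6.2 and 6.3 with Protocol 8.3.1 and 8.3.4.
4. Carry the general provision of Protocol 13.4 into SAP 7.3 for baseline covariates, for example by filling a missing baseline with the population-stratum mean pooled over arms and keeping the person in the model. The 7.2.1 model and the planned INQ and stress changes need this rule in any case.

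The cost is a few sentences and one covariate per model, with no new data. The downside is the possible loss of precision against raw change when baseline SD is low and correlation high: a few percent if scores are imputed, more if the alternative would have been a raw change from imputed changes.

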7.2.3 Subgroups

The primary outcome will be summarized in subgroups defined by:

- Age category: older adult (50+) vs. adult (26-49) vs younger adult (18-25) vs adolescent patients (<18),
- types of providers (patient-facing providers [physicians and APP; pharmacy, PAS, lab, specialists, technicians, MAs;; nursing; social support services] vs. non-clinical [office work and educators; senior management; and other]),
- baseline suicide risk (low baseline C-SSRS score vs moderate to high baseline C-SSRS score),
- Hispanic vs non-Hispanic,
- female vs male sex at birth,
- cisgender vs transgender or gender-nonconforming,
- heterosexual vs. homosexual, bisexual, or other, and
- urban vs rural.

7.2.4 Safety analysis

The number and proportion of subject experiencing the listed safety events, as well as any other reported safety events, will be summarized by cohort and treatment arm.

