5.4 Populations for Analyses

Analyses will be completed using the following populations:

1. **Intention to Treat (ITT) Analytic Population:** Data for all participants that complete study enrollment will be included in this dataset.
2. **Safety Analysis Population:** The dataset shared with the Data & Safety Monitoring Board for safety analysis will include data for all participants who completed study enrollment (e.g., the ITT Analytic Population Dataset).
3. **Per-Protocol Analysis Population:** Data for a subset of participants who were retained for the full study, were sent all 11 caring text messages, and received a phone call if randomized to the CC+ intervention (as outlined in protocol section 9) will be included in this dataset.
4. **Additional populations:** Additional datasets may be developed to complete sensitivity analyses, for example, where missing data have been imputed using different techniques.

6. Study Procedures

Aim 1: Cross Sectional Survey (Email REDCap survey link for providers and staff; send REDCap survey link via MyChart or email for patients)

- Aim 1 study enrollment and informed consent
- Aim 1 Survey
 - Demographics questions
 - C-SSRS (suicide risk)
 - NIH Toolbox Social Relationship Scales (loneliness, stress)
 - INQ (defeat, entrapment, perceived burdensomeness, and thwarted belongingness)
 - PHQ-9 (depression)
 - GAD-7 (anxiety)
 - COVID-19 beliefs and practices survey (brief)

Aim 2: Baseline / Enrollment (Subset of Aim 1 participants; see below)

- Aim 2 study enrollment and informed consent (phone call with Research Coordinator or study staff to complete via REDCap)
- Aim 2 Baseline assessments (Email or text REDCap survey link)
 - Baseline survey (Socio-economic status, gender identity, sexuality, religion, and alcohol and illicit drug use)
 - Expanded COVID-19 beliefs and practices survey (additional questions related to impact of COVID-19 on the individual, and his/her/their family, friends, and community)
 - Contact Sheet to collect alternative forms of contact for study participant

Aim 2: Caring Contacts Interventions (see description of interventions in section 9)

- **CC+:** 1 call, within 2 weeks of enrollment, and 11 caring text messages, sent from Hotline

follow-up specialists according to a standardized schedule over a 6-month period

- **CC:** 11 personalized caring text messages sent from Hotline follow-up specialists according to a standardized schedule over a 6-month period

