11.3 Safety Outcomes

This protocol considers completed suicide, suicide attempts, and inpatient admission in the context of highly suicidal study participants as expected events. These will be routinely tracked as key safety outcomes. The following safety outcomes will be assessed for each participant at 3 and 6 months and reviewed by the Data and Safety Monitoring Board twice annually to determine whether the rate of safety outcomes differs by intervention arm:

- Death by suicide
- Attempted suicide
- Interrupted or aborted suicide attempt
- Psychiatric hospitalization for anxiety, depression, and/or suicidal ideation
- Medical hospitalization related to self-harm or attempted suicide
- Medical hospitalization related to unintentional overdose or substance use disorder

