11.4 Adverse Events and Serious Adverse Events

This protocol does not include tracking of adverse events (AEs). This protocol does not include real-time tracking of serious adverse events (SAEs) for several reasons. First, as stated above, the most important events that would be defined as SAEs are expected safety outcomes in the context of study participants experiencing suicidality or other forms of mental distress. All deaths of study participants will be reviewed and assessed to determine whether the cause of death is suicide. We do not anticipate any SAEs beyond those listed as safety outcomes above, but unanticipated SAEs that occur will be reviewed by the DSMB and the IRB. Second, this research compares two models of an evidence-based intervention that has been widely studied, has an established safety record, and is already in widespread

clinical practice. This is not an experimental, novel, or untested intervention with unknown safety outcomes. Finally, the most important safety question to ascertain in the context of this trial is whether rates of safety outcomes or SAEs are differential across the two intervention groups. This protocol will monitor safety outcomes collected at 6 months as part of routine study outcome assessments through regular DSMB meetings to ensure equal ascertainment of outcomes across intervention groups. This is the most valid and reliable way to review safety data in the context of this pragmatic clinical trial.

12. Data Collection & Management

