Variables will be measured through the Aim 1 survey or Aim 2 Baseline survey and reported using descriptive statistics. Potential effect modifiers will be assessed and include age, sex, gender identity, sexuality, race/ethnicity, religion, employment, urban/rural residence, drug/alcohol use, suicidal ideation at baseline, baseline depression score, baseline anxiety score, baseline stress score, baseline quality of life, measures of socioeconomic status and/or other variables related to the specified outcomes of interest. Data will be analyzed according to both an intention to treat protocol and per protocol received. Please see section 5.4 *Populations for Analyses* for further detail.

This study will report the distribution of key variables to facilitate assessment of the study's internal and external validity. At a minimum, this study will report the distribution of key variables within the analytic population (key variables are defined as those that are included in the causal diagram at the beginning of the *Research Design* section of this Research Plan). Missing data will be assessed on a regular basis through routine data reports. These reports will allow the investigators to assess the cause of missing or anomalous entries, and address these if possible. If missing values cannot be retrieved, the reason for the missingness will be recorded in data comments available through REDCap. Study staff will record the reason for any participant drop-out during the 6 months of follow-up.

[13.2 Power & Sample Size for Aim 2](#)

The total sample size for the aim 2 trial is 660 participants. For each stratum (patients, providers/staff), a sample of 330 subjects (165 in each arm) allows 80% power to detect a difference of 5 units in the primary outcome (loneliness) if a minimum of 70% of participants are retained through study completion.

[13.3 Duplicate Surveys](#)

A data cleaning step will be included to identify surveys completed twice by the same individual. This may occur, for example, when an individual is both a provider/staff person and a patient at SLHS. If duplicate surveys are identified, the first will be retained, and the second will be excluded from the research.

[13.4 Missing Data](#)

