5.3 Analysis Populations

1. Aim 1: All participants who complete the survey will be included in the data tabulations.
2. Aim 2:
 - a. **Intention to Treat (ITT) Population:** Data for all participants that complete study enrollment and the baseline survey will be included in this dataset. The primary and secondary endpoints will be evaluated in this group.
 - b. **Safety Analysis Population:** All safety analysis will include all participants who completed study enrollment and the baseline survey (equivalent to the ITT population).
 - c. **Per-Protocol Analysis Population:** The per-protocol analyses will include the subset of participants who were retained for the duration of the study and completed the assigned intervention as outlined in protocol section 9.
 - d. **Additional Populations:** Additional populations may be used to complete sensitivity analyses, for example, where missing data have been imputed using different techniques.

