6.4 Safety Outcomes

This protocol considers completed suicide, suicide attempts, and inpatient admission in the context of highly suicidal study participants as expected events. These will be routinely tracked as key safety outcomes. The following safety outcomes will be assessed for each participant at 6 months and reviewed by the Data and Safety Monitoring Board twice annually to determine whether the rate of safety outcomes differs by intervention arm:

- Death by suicide
- Attempted suicide
- Interrupted or aborted suicide attempt
- Psychiatric hospitalization for anxiety, depression, and/or suicidal ideation
- Medical hospitalization related to self-harm or attempted suicide
- Medical hospitalization related to unintentional overdose or substance use disorder

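### Safety proportions are set on everyone with a baseline survey, but most listed events are ascertained mainly at the 6-month survey; with no rule for non-responders, rates would fall with retention

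*SAP*

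**What the plan says.** **Summary planned.** SAP 7.2.4 promises "The number and proportion of subject experiencing the listed safety events". Events that come to notice in other ways are added, and the table is split by arm and cohort. That section names no denominator.

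**Denominator.** SAP 5.3, item 2b, supplies it: "All safety analysis will include all participants who completed study enrollment and the baseline survey". Protocol 5.4 is slightly wider; the dataset for the monitoring board "will include data for all participants who completed study enrollment". Neither requires a 6-month response.

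**Ascertainment.** Protocol 11.4: "This protocol will monitor safety outcomes collected at 6 months as part of routine study outcome assessments". SAP 6.4 agrees: "The following safety outcomes will be assessed for each participant at 6 months". Protocol 11.3 differs: "The following safety outcomes will be assessed for each participant at 3 and 6 months". Protocol Table 1 shows no 3-month survey, but it does mark safety reporting from weeks 0-2 onward. Deaths have their own source, vital records (Protocol 8.3.1 and Table 2; SAP Table 1), and Protocol 11.4 has every death reviewed for cause.

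**Retention.** The power statement in Protocol 13.2, repeated in SAP 5, holds "if a minimum of 70% of participants are retained through study completion".

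**Missing data.** SAP 7.3 imputes missing 6-month outcomes by hot deck and does not name safety events. SAP 7.4 limits its sensitivity analyses to the primary results.

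**The concern.** The denominator counts people whose safety status at 6 months may be unknown. If a non-responder adds one to the denominator and cannot add to the numerator, the proportion falls as retention falls, and a retention gap between arms appears as a gap in safety.

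Protocol 11.4 calls a difference in safety rates between arms the most important safety question and says that its approach gives equal ascertainment. The board is to judge whether rates differ by arm. An introductory call could plausibly change who answers the 6-month survey, and people in crisis may answer less often; the documents report on neither. SAP 7.4 foresees missingness that reflects poor outcomes or varies by arm, but applies that only to the primary results.

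**Working it through.** **The plan's own figures.** The documents give no expected safety rate and no safety power. The only power figure is 80% for a 5-unit loneliness difference with 165 per arm. It cannot be reproduced because no SD is stated. With 165 × 0.70 = 115.5 retained per arm, 80% power needs SD = 5 / [(1.960 + 0.842) × √(2/115.5)] ≈ 13.6. Nothing below depends on this.

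**Inputs.**
- Retention r: 70% is the planning minimum (Protocol 13.2, SAP 5). Splits by arm are assumptions.
- True event rate p: 2%, 5% and 10% are assumptions.
- n = 165 per arm per cohort.
- Working condition: non-responders stay in the denominator and add no events. The documents do not state this.

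**Step 1: level.** If response is unrelated to events, observed proportion = p × r. At r = 0.70:
- 0.02 × 0.70 = 1.4%
- 0.05 × 0.70 = 3.5%
- 0.10 × 0.70 = 7.0%

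The relative understatement is 1 − r = 30% in each case.

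**Step 2: comparison, equal true rates.** Apparent ratio = (p × r₁)/(p × r₂) = r₁/r₂, whatever p is.

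| Retention (assumed) | Apparent ratio | Shown at p = 5% | Events per 165 |
|---|---|---|---|
| 75% vs 65% | 1.15 | 3.75% vs 3.25% | 6.2 vs 5.4 |
| 80% vs 60% | 1.33 | 4.0% vs 3.0% | 6.6 vs 5.0 |
| 85% vs 55% | 1.55 | 4.25% vs 2.75% | 7.0 vs 4.5 |

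**Step 3: masking.** True rates of 10% and 7.5% with retention of 60% and 80% give 0.10 × 0.60 = 6.0% and 0.075 × 0.80 = 6.0%. The difference disappears.

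**Step 4: chance of formal significance.** At p = 10% and 80% vs 60% retention (8.0% vs 6.0%), a two-sided 5% test of two proportions is significant in that direction about 11% of the time with 165 per arm and 17% with 330 per arm, against 2.5% with equal retention. At p = 2% the figures are about 5% and 6%.

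**Step 5: what a responder denominator does.** If response is unrelated to events, it returns p in both arms. If people with events respond less, it does not. With p = 10%, 50% response among those with events and 70% overall, the full set shows 0.10 × 0.50 = 5.0% and responders show 0.05/0.70 = 7.1%. It is closer, but still low.

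**The case against.** The strongest reply is that no text codes a non-responder as event-free. SAP 5.3 says whose data enter the safety analysis, and a missing item could be tabulated as missing. A reader might infer that the plan does count non-responders as free of events, so that rates are certain to be understated. The documents do not support that; the result is conditional. SAP 7.3 can also be read to cover safety outcomes, since SAP 6.4 assesses them at 6 months. Imputation within arm and cohort would then return roughly the responder rate, and neither distortion would arise. Against that reading, SAP 7.2.1 points to 7.3, whereas 7.2.4 does not.

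A reader might also infer that events are seen only in survey responders. That is too strong. Deaths come from vital records, Protocol Table 1 marks safety reporting throughout follow-up, Protocol 11.3 mentions 3 months, and SAP 7.2.4 adds other reported events. Mainly is the right word: no separate source is named for the other five listed outcomes. Other capture may itself differ by arm, because the CC+ call can include a wellbeing check (Protocol 9.1) and CC has no such call.

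Three further points stand. The 70% is a condition of the power statement and not a forecast. The retention splits are assumed, and at a 5% rate they amount to between one and three events per 165. The summary is descriptive, and the board also reviews retention and data completeness (Protocol 11.2). These limit the size of the problem; they do not supply the missing rule.

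**Conclusion.** The concern holds in conditional form and is worth correcting before analysis. The stated safety set, applied literally to events ascertained mainly at 6 months, multiplies each rate by retention (a 30% relative understatement at the planning minimum) and turns a retention ratio into an apparent risk ratio. This rests on three assumptions: missing safety items are neither imputed nor shown as missing, little is captured outside the survey, and response is unrelated to events. Event rates and retention by arm are illustrative because the documents give none. A spurious significant result is unlikely; the harm is to a table that will be read descriptively on the question that the protocol ranks first. Deaths are not affected, and the full denominator suits them.

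**What to change.** In SAP 5.3 (item 2b) and 7.2.4:

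1. Show the number assessed for safety at 6 months by arm and cohort, and use it as the denominator for survey-ascertained events.
2. Keep the full safety population for deaths from vital records.
3. List events reported outside the survey separately, as counts by arm, so that numerator and denominator match.
4. Give the arm difference with a 95% CI.
5. State how missing safety items are handled, including whether 7.3 applies, and add a sensitivity analysis for them. If one scenario counts non-responders as events, label it an extreme bound: at an assumed 5% and 70% retention it gives 3.5% + 30% = 33.5%.
6. Reconcile the 3- and 6-month assessment in Protocol 11.3 with the 6-month assessment in Protocol 11.4 and SAP 6.4.

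The cost is SAP wording and one extra table. Reported rates will rise, for example from 3.5% to 5%, which is 0.05/0.035 = 1.43 times. The responder denominator stays biased if people with events respond less, which is why item 5 is needed.
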